15.2 Informed Consent Process

Prior to the administration of any tests or procedures required in this protocol for either the Screening or Active Phase, the investigator or designee will obtain informed consent in writing from all potential subjects considered for entry into this trial. Each patient must sign and personally date the informed consent. Copies of the informed consent will be retained in the medical record and the subject's study binder. A copy of the signed informed consent will be given to the subject to take home.

The consent form and as necessitated by local law, an additional patient information leaflet for study participation, will explain the nature of the study, its objectives and potential risks. Furthermore, it will detail the requirement of the participant, the trial treatment and the probability for random assignment to each treatment group, all trial procedures, alternative procedures and the fact that he is free to withdraw his consent at any time without reason. Details of indemnity and insurance are also attended with assurance.

CONFIDENTIAL	Clinical Protocol	DATE 9Dec2019	P	age
	mented Disc Regeneration in the T reatment of th or without Intervertebral Disc Herniation –	WRITER TG, DB, PW	NO. 49	REV 6

As required by ICH-GCP the subject will give in writing his authorization that the study data may be given for review to the responsible authorities, and that the monitor will be granted direct access to the subject's original medical records for verification of clinical data.

Notification to Authorities

The study protocol together with the investigators' names, the investigation sites and the votes of the Ethic Committees will be presented to the responsible health authorities and retained by the sponsor.

15.3 Steering Committee

A Steering Committee will be established for the conduct of the study with the purpose to observe the course of the study and to ensure the highest possible safety for each participating patient. The data to be reviewed, and the timing of the review/s, will be defined in the Steering Committee mission and guidance documents.

In particular, the Steering Committee will receive the 1-Month data for the first 24 randomized patients and will determine based upon this information if the recruitment of the remaining 196 subjects can continue. Participants in the steering committee will include [name], MD, a neurosurgeon, and [name], MD, an interventional radiologist, and be chaired by H [name], Chief Medical Officer for Vivex Biologics, Inc.

15.4 Site Selection and Qualification

A qualification and selection visit will be performed to evaluate site facilities, investigator qualifications, adequacy of staffing, and understanding of clinical and regulatory requirements.

15.5 Site Initiation

All investigators and appropriate study staff will be required to participate in an investigator meeting which will provide training to all sites at one time or if applicable onsite training in order to provide orientation and training regarding the device operation and applicable procedures, protocol and CRFs. Physicians and office staff necessary to execute the trial will be trained to the composition of the test article, to the history of the implant in intervertebral disc therapy, and then provided a laboratory course in preparation of the allograft which will include mixing, placement in syringe, and delivery into the center of the disc. Injected discs will be imaged, planed with a band saw (if at UMTB facility), and distribution confirmed to depict the intended distribution of the material in a clinical setting.

CONFIDENTIAL	Clinical Protocol	DATE 9Dec2019	P	age
	mented Disc Regeneration in the T reatment of th or without Intervertebral Disc Herniation –	WRITER TG, DB, PW	NO. 50	REV 6

15.6 Monitoring

During the course of the study, the sponsor or designee may make site visits to review protocol compliance, perform source data verification, assess test article accountability, and ensure compliance with pertinent regulatory requirements. All review of medical records will be performed in a manner to ensure that patient confidentiality is maintained.

Satisfactory verification of CRF completion, source document verification and query resolution may be required to monitor the progress of the study. Moreover, regulatory authorities may wish to carry out such source data checks and/or on-site audit inspections with reasonable notification to the study site. Direct access to source data will be required for these inspections and audits; they will be carried out giving due consideration to data protection and medical confidentiality.

15.7 Required Reports

The following reports are required of the investigator:

- Reports to Pharmacovigilance (appointed by Sponsor) of any SAEs immediately or at least within 24 hours of the study site becoming aware of such events
- Reports to the sponsor and the reviewing EC of any UADEs within 10 working days of
 the study site becoming aware of events (unless the UADE is a serious event, in which
 case it must be reported to the sponsor immediately or at least within 24 hours of the
 study site becoming aware of such events)
- Report to the sponsor, within 5 working days, of withdrawal of approval by the reviewing EC or regulatory authority
- Progress reports to the sponsor, monitor, and the reviewing EC at regular intervals (at least yearly)
- Report to the sponsor and the reviewing EC of any deviation from the protocol to
 protect the life or physical well being of a patient in an emergency situation. Such
 notice will be given as soon as possible, but in no event later than 5 working days after
 the emergency occurred
- Reports of any study procedure(s) being performed without prior written informed consent being obtained. Such notice will be given to the sponsor and the reviewing EC within 5 working days of the study procedure(s) being performed

CONFIDENTIAL	Clinical Protocol	DATE 9Dec2019	P	age
	mented Disc Regeneration in the $\underline{\mathbf{T}}$ reatment of th or without Intervertebral Disc Herniation –	WRITER TG, DB, PW	NO. 51	REV 6

- Final report submitted to the sponsor and the reviewing EC as soon as possible, but no later than 3 months, after the conclusion of the study or the conclusion of the investigator's participation in the study
- Other reports to the reviewing EC as may be required

CONFIDENTIAL	Clinical Protocol DATE		Page	
3311122111111		9Dec2019		
	mented Disc Regeneration in the T reatment of th or without Intervertebral Disc Herniation –	WRITER TG, DB, PW	NO. 52	REV 6

16 STUDY REQUIREMENTS

To protect the rights and welfare of subjects, the study will be conducted in conformance with the Declaration of Helsinki, the ICH E6 guidelines on Good Clinical Practice (GCP), and/or the laws and regulations of the participating country, whichever affords the greater protection to the human patient.

All investigators, sub-investigators and study personnel are required to read and follow the protocol, as well as any literature that accompanies the products prior to conducting the study procedure for the first time. All investigators participating in this study will be required to be trained in the proper use of the study procedures and in the components of this protocol by the sponsor.

The PI is ultimately responsible for the conduct of this study; however, he/she may designate a member or members of his/her staff to assist with the collection of data and completion of CRFs. The designee(s) will be documented on an authorization form that is signed by the PI and kept in the Regulatory Binder, to be updated as necessary.

Obtaining informed consent in accordance with national policy is mandatory for patient participation. All patient data is kept confidential and procedures will be implemented to ensure that patient confidentiality is not compromised.

If alternative consent materials are used, they must be approved by Vivex Biologics, Inc. at the clinical site prior to use. Documentation of the approved informed consent must be provided to Vivex Biologics, Inc. prior to study commencement at the clinical site.

After Informed Consent has been obtained, all screening procedures have been performed, and eligibility for the study has been confirmed, the subject will be considered enrolled in the study. After this point, the reason(s) must be documented on the CRF for any patient who has dropped, withdraws, or for any reason cannot complete this study.

16.1 Quality Assurance

All data concerning the study will be documented on the patient's medical record and on CRFs designed especially for this study, or on data clarification forms (DCFs) if necessary. Each CRF and DCF will consist of an original plus two copies.

In line with ICH-GCP guidelines, clinical monitors will arrange regular visits to the trial center(s) to check progress with the study and to collect completed CRFs. One copy will remain in the study center, the original will be passed to Vivex Biologics, Inc. or designated representative for data management. The original will be send to the sponsor at the end of the study. Until then,

CONFIDENTIAL	Clinical Protocol		Р	age
		9Dec2019		
	mented Disc Regeneration in the T reatment of h or without Intervertebral Disc Herniation –	WRITER TG, DB, PW	NO. 53	REV 6

the originals will remain at Vivex Biologics, Inc. or designated representative for data management. The CRFs will be checked for completeness and plausibility by the clinical investigator and the monitor (manually) as well as by Vivex Biologics, Inc. or designated representative for data management.

In addition, the representatives of the Clinical Quality Assurance department at the sponsor, of the CRO, and of regulatory authorities, are permitted to inspect the study documents (Study Protocol, Case Report Forms, study medication, original medical records/files). All patient data shall be treated confidentially.

In order to guarantee that the performance of the study is in accordance with the ICH-GCP stipulations, in-house and on-site Audits may be carried out. Study protocol and final report will be additionally examined by the Quality Assurance Unit of the sponsor and/or Vivex Biologics, Inc. or designated representative for data management.

The investigator agrees to give the auditor access to all relevant documents for review. The same applies in case of an inspection the authorities.

After every on-site audit the investigator will receive an audit confirmation by the auditor. This has to be filed together with the study documentation and be made available to the authorities in case of supervision. At the end of the study, audit certificates will be included in the final report.

16.2 Monitoring

It is the responsibility of the investigator to assure that the study is conducted in accordance with the protocol and that valid data are entered into the CRF.

The investigator will permit a representative of Vivex Biologics, Inc. or designated representative for data management to monitor the study as frequently as necessary to determine that data recording, and transplant handling and protocol adherence are satisfactory. The CRFs and related documents will be reviewed in detail in accordance with the SOPs of Vivex Biologics, Inc. or designated representative for data management and Good Clinical Practice regulations (ICH-GCP).

In fulfillment of their obligation to the sponsor to verify compliance with this protocol, Vivex Biologics, Inc. or designated representative for data management will require that the investigator permits the monitor and/or the sponsor's monitor to review that portion of the patient's primary medical records which directly concern this study.

CONFIDENTIAL	Clinical Protocol DATE		P	age
		9Dec2019		
TITLE: V iable A llograft S upplemented Disc Regeneration in the T reatment of Patients with Low Back Pain with or without Intervertebral Disc Herniation –			NO. 54	REV 6
VAST-001-017	and without meet vertees at 213c Hermation		01	

It is the investigator's obligation to ensure that documentation of all relevant data such as medical history/concomitant diseases, date of study enrollment, visit dates, results of examinations, administrations of medication and adverse events is correctly entered in the patient's file.

Vivex Biologics, Inc. or designated representative for data management will affirm and uphold the principle of the subject's right to protection against the invasion of privacy. Throughout the study, all data will only be identified by patient number, patient initials and date of birth. Anonymity of the data will be maintained in all data analyses.

All obtained data will be checked for plausibility and completeness by the monitor and in-house by Vivex Biologics, Inc. or designated representative for data management.

CONFIDENTIAL Clin	Clinical Protocol		Clinical Protocol DATE		P	age
TITLE: V iable A llograft S upplemented Disc Regel Patients with Low Back Pain with or without Intel VAST-001-017	-	WRITER TG, DB, PW	NO. 55	REV 6		

17 PROCEDURES AND INSTRUCTIONS

17.1 Special safety-related procedures

No special safety-related procedures, other than those attending the risks of surgery, need to be defined. In the case of complications/emergency, physicians will use their clinical judgment on the best course of action. All complications related to supplemental allograft transplantation will be documented by the physician and will be forwarded to Vivex Biologics, Inc.

17.2 Administrative procedures

Vivex Biologics, Inc. will be responsible for the supply of Vivex Biologics, Inc. equipment and will provide training on the use for the mixture of the supplemental transplant allograft. A Vivex Biologics, Inc. representative will be present for the initial 2 implantations at each site to ensure proper procedure is followed. Once the site has experience in randomization, data collection, and allograft delivery as determined by Vivex Biologics, Inc., on-site support will be available on request and through a 24-hour phone system. The interventional procedures will be performed by experienced centers and physicians named by Vivex Biologics, Inc. to ensure the highest quality of the implantation.

17.3 Ethics and Good Clinical Practice

The study will be conducted in accordance with the ICH Guideline for Good Clinical Practice and the appropriate regulations of relevant national regulations and the Declaration of Helsinki (revised version of Edinburgh, Scotland, October 2000).

CONFIDENTIAL	Clinical Protocol	DATE 9Dec2019	Pa	ige
	mented Disc Regeneration in the $\underline{\mathbf{T}}$ reatment of th or without Intervertebral Disc Herniation –	WRITER TG, DB, PW	NO. 56	REV 6

APPENDIX A - STUDY SCHEDULE

Visit	VS1 ^a	VA1 ^a	VA2 ^b	VA3 ^c	VA4	VA5	VA6	VA7
Visit Window	Screening (Day -14 to 0)	Day 0	1 month (±3 Days)	3 months (±14 Days)	6 months (± 30 Days)	12 months (+ 30 Days)	24 months (± 3 Months)	36 months (± 3 Months)
Informed Consent	Х						Х	
Eligibility Criteria	Х							
Eligibility Criteria Check		Х					х	
Randomization		Х						
Injection Treatment (Allograft or Saline)		Х					X ^f	
Demographic Data	х							
Medical History	х							
Physical Examination		Х	х	Х	Х	Х	X ^f	
Neurological Examination		Х	Х	X	X	X	Χ ^f	
MRI and X-ray Evaluations	X		X	X ^d	X e	X	X ^f	
Laboratory Investigation	Х		Х	Х	Х	Х	X ^f	
Urine/Pregnancy Test, if applicable		Х						
VASPI Questionnaire	х		х	Х	х	х	х	Х
SF-36 Questionnaire	x		х	х	х	х	х	x
ODI Questionnaire	х		х	Х	х	х	х	х
Resource Utilization	Х				Х	Х	Х	Х
Concomitant Medication	Х	Х	Х	Х	Х	Х	Х	Х
Adverse Events		Х	х	Х	Х	Х	Х	Х

^a VS1 and VA1 may both occur on Day 0.

^b Month 1 Visit (VA2*) to be performed for the first 24 subjects randomized only.

CONFIDENTIAL	Clinical Protocol	DATE 9Dec2019	Pa	ige
	mented Disc Regeneration in the $\underline{\mathbf{T}}$ reatment of th or without Intervertebral Disc Herniation –	WRITER TG, DB, PW	NO. 57	REV 6

^c Subjects randomized to conservative care will be evaluated at 3 months to assure they are not experiencing further debilitating changes. During this visit, subjects may be offered crossover to allograft treatment. To administer the crossover allograft treatment, a new visit will be scheduled and this visit will be considered as the new Active Phase Day 0 (VA1).

^d MRI and X-ray to be done in the event a subject crosses over from conservative care to the Allograft treatment.

^e At the 6-month follow-up visit, subjects will be randomized to receive a MRI, (1:1 ratio). Crossover subjects to allograft treatment will all receive an MRI at the 6 month visit after allograft treatment. All subjects will receive an X-ray at the 6 month follow up visit.

f At the 24-month in-office visit, subjects will first be reevaluated for inclusion/exclusion and fill out VASPI, ODI, SF-36, and Resource Utilization. If eligible for allograft treatment, the PI will perform a neurological exam, physical exam, laboratory investigation, and MRI/X-ray.

[figure not shown]
CONFIDENTIAL	Clinical Protocol DATE		Page	
99111 12 E111111 12		9Dec2019		
	mented Disc Regeneration in the $\underline{\mathbf{T}}$ reatment of th or without Intervertebral Disc Herniation –	WRITER TG, DB, PW	NO. 58	REV 6

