Optional long term follow up at 24 and 36 months for all randomized subjects will allow for additional secondary endpoints to analyze pain. Subjects who wish to participate in the long term follow up will reconsent with the informed consent addendum 2 during an office visit. Subjects then will be reassessed for inclusion/exclusion criteria and fill out VASPI, ODI, SF-36, and Resource Utilization questionnaires. If eligible for an allograft injection, the PI will perform a neurological exam, physical exam, labs, and give the subject applicable questionnaires. An MRI and x-ray will be performed on subjects receiving another injection for safety purposes.

CONFIDENTIAL	Clinical Protocol	DATE 9Dec2019	P	age
	mented Disc Regeneration in the T reatment of th or without Intervertebral Disc Herniation –	WRITER TG, DB, PW	NO. 25	REV 6

The 36-month visit can be performed over the telephone by the study coordinator if the subject wishes.

Figure 1 – Study Design

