7.1.4 Conservative Treatment Group 3 Months (± 14 days), or VA3

Patients randomized to the conservative arm will be evaluated with VASPI, ODI, SF-36 questionnaires as well as complete all required additional assessments as outlined in Appendix A during the 3 months visit. Patients will be evaluated for deteriorating or improving conditions relative to enrollment. Subjects who have experienced a significant decline in condition defined as a 10% increase in pain by VASPI, or a 9-point increase in ODI will be offered the allograft treatment as a crossover. If the subject does not meet the aforementioned changes in ODI or VASPI, or is considering withdrawal, they may also be offered the allograft treatment by physician discretion if condition has significantly declined. Subjects that crossover do not have to re-consent. The crossover allograft treatment can occur at any time period after the 3-month follow-up visit. To administer the crossover allograft treatment, a new visit will be scheduled and this visit will be considered as the new Active Phase Day 0. In addition to the 3 months follow-up visit assessments, these crossover subjects will receive a MRI and X-ray prior to the allograft treatment. All assessments done at this 3 months follow-up visit will be considered as the new baseline assessments. These crossover subjects will receive follow-up visits at 6 months and 12 months after allograft treatment. Crossover subjects will not be replaced by enrolling new patients in the conservative care treatment group.

7.1.5 Active Phase Month 6 (± 30 days) or VA4:

All randomized subjects will return to the clinic 6 months (± 30 days) subsequent to treatment for all safety and efficacy assessments as outlined in Appendix A. ODI, VASPI, and SF-36 questionnaires will be completed by the subject, and assisted by physician or physician designee. All subjects (excluding conservative care crossover subjects) will be randomized to include MRI at 6-month (MRI or no MRI, ratio 1:1) follow-up in addition to all other assessments. This randomization is performed to assess whether predictability at 6 months indicates performance at 12 months. The conservative care subjects that crossover to the allograft treatment group will all receive an MRI at 6-month follow-up after allograft treatment. All subjects will receive an X-ray at the 6-month follow-up visit. Additionally, a review of resource utilization since the Day 0 visit will be completed.

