CONFIDENTIAL	Clinical Protocol	DATE	Р	age
		9Dec2019		T
TITLE: V iable A llograft S upplemented Disc Regeneration in the T reatment of		WRITER TG, DB, PW	NO.	REV
Patients with Low Back Pain with VAST-001-017	th or without Intervertebral Disc Herniation –	. 0, 22,	31	6

7.1.6 Active Phase Month 12 (+ 30 days) or VA5:

All randomized subjects will return to the clinic 12 months (+ 30 days) subsequent to transplantation for safety and efficacy assessments as outlined in Appendix A. ODI, VASPI, and SF-36 questionnaires will be completed by the subject, with assistance from physician or physician designee. All subjects will receive an MRI and X-ray at the 12-month follow-up visit. A review of resource utilization through the 12 Month visit will be completed.

7.1.7 Optional Long-Term Follow Up Month 24 & Month 36 (+ 3 Months) or VA6 & VA7:

All randomized subjects will have an option to continue to be monitored for long-term follow up. Before study procedures begin, the informed consent addendum 2 for study extension will need to be signed. At the 24-month in-office visit, subjects will first be reevaluated for inclusion/exclusion and fill out VASPI, ODI, SF-36, and Resource Utilization. If eligible for allograft treatment, the PI will perform a neurological exam, physical exam, labs, and give the subject applicable questionnaires. All randomized subjects will have the option to receive allograft treatment at 24 months in accordance with the inclusion/exclusion re-evaluation. An MRI and x-ray will be performed on subjects receiving another injection for safety purposes. If needed, a second office visit may be scheduled within 14 days of the original evaluation to allow appropriate time for the laboratory investigation and MRI. All follow up subjects will complete VASPI, ODI, SF-36, and Resource Utilization questionnaires at both follow up visits. The 36-month will consist of questionnaires and can be performed over the phone if the subject chooses.

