8.6 Study Schedule

The Study Schedule with all required assessments is listed in Appendix A.

CONFIDENTIAL	Clinical Protocol	DATE	Р	age
		9Dec2019		ı
TITLE: $\underline{\mathbf{V}}$ iable $\underline{\mathbf{A}}$ llograft $\underline{\mathbf{S}}$ upplemented Disc Regeneration in the $\underline{\mathbf{T}}$ reatment of		WRITER TG, DB, PW	NO.	REV
Patients with Low Back Pain wit VAST-001-017	th or without Intervertebral Disc Herniation –	10, 00, 1 W	39	6

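### The optional Month 24 allograft injection has no scheduled pregnancy test, although the same schedule requires one (if applicable) at the Day 0 injection

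*Protocol*

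**What the plan says.** Protocol section 8.6 makes the schedule the controlling list: "The Study Schedule with all required assessments is listed in Appendix A". In that schedule the injection row is marked at VA1 and, with footnote f, at VA6. The row "Urine/Pregnancy Test, if applicable" carries a single mark, at VA1.

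The Month 24 work-up before an injection is described in three places:

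- Appendix A, footnote f: "If eligible for allograft treatment, the PI will perform a neurological exam, physical exam, laboratory investigation, and MRI/X-ray".
- Section 7.1.7: "If eligible for allograft treatment, the PI will perform a neurological exam, physical exam, labs, and give the subject applicable questionnaires".
- Section 6: "If eligible for an allograft injection, the PI will perform a neurological exam, physical exam, labs, and give the subject applicable questionnaires".

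The injection is offered widely. Section 7.1.7 says: "All randomized subjects will have the option to receive allograft treatment at 24 months in accordance with the inclusion/exclusion re-evaluation". It also provides that, if needed, "a second office visit may be scheduled within 14 days of the original evaluation to allow appropriate time for the laboratory investigation" and the MRI.

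The conservative-care crossover injection is handled differently. Under section 7.1.4, "a new visit will be scheduled and this visit will be considered as the new Active Phase Day 0", and footnote c of Appendix A labels that visit VA1.

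The only pregnancy-related eligibility criterion (section 8.1) is an agreement to use contraception together with no plan to become pregnant in the 24 months after treatment. Pregnancy is not among the exclusions in section 8.2.

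**The concern.** At Day 0 the schedule requires both an eligibility check and a pregnancy test where applicable. At Month 24 it keeps the check and leaves out the test, although the same product goes into the disc. No reason is given. Nearly every other element of the pre-injection work-up was carried to VA6, so this looks like a row overlooked when the extension was added, not a decision.

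What is at stake is the safety of a subject, and possibly of a fetus. The trial enrols men and women aged 18 to 60. Section 12 acknowledges that there are no clinical data on this allogeneic material in this population. Section 14.1 lists immunological response and transmission of infectious agents among the expected adverse events. A site that follows the visible plan exactly could inject a subject at Month 24 whose pregnancy status is unknown.

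**Working it through.** The plan gives no figure to reproduce. The check sets the schedule rows side by side and then looks for any other text that supplies the test.

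**Step 1. The schedule at the two injection visits (Appendix A).**

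| Row | VA1 (Day 0) | VA6 (Month 24) |
|---|---|---|
| Injection | X | X, footnote f |
| Eligibility check | X | X |
| Physical examination | X | X, footnote f |
| Neurological examination | X | X, footnote f |
| MRI and X-ray | done at screening | X, footnote f |
| Laboratory investigation | done at screening | X, footnote f |
| Pregnancy test, if applicable | X | blank |

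The pregnancy row reads cleanly: one mark in the second visit column and six empty cells after it. Table damage from PDF extraction is an unlikely explanation.

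**Step 2. Does other text supply the test?**

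- Footnote f and sections 6 and 7.1.7 name examinations, laboratory work, imaging and questionnaires between them. None names a pregnancy test.
- The reference to laboratory work does not bring one in. The section 8.5 panel consists of hematology, clinical chemistry and PTT.
- Section 8.4.1 carries only the recording of procedure details over to the placebo crossover visit.

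**Step 3. Does the eligibility re-check do the same job?** The criterion re-checked is an agreement and an intention, and a subject can meet it truthfully while unknowingly pregnant. VA1 has the check and the test together, so the schedule does not treat one as replacing the other.

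**Step 4. Could the Day 0 result still serve?** Appendix A gives VA6 a window of 24 ± 3 months: 24 − 3 = 21 and 24 + 3 = 27. A test at the original Day 0 is therefore 21 to 27 months old. A result from a later crossover visit would be more recent, but it still describes status at the earlier injection, not at VA6.

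**Step 5. The crossover injection.** Coverage here is inferred. The visit is labelled a new Day 0 (VA1), which would bring in the VA1 rows. But VA1 also carries randomization, which is not repeated at crossover, so the label cannot mean every row. Section 7.1.4 describes the crossover work-up as the 3-month assessments plus MRI and X-ray and does not mention a pregnancy test. The test is implied, not stated.

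**Step 6. Action on a positive result.** The visible text gives none for any injection, and pregnancy is not an exclusion.

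**The case against.** The strongest reply is that several safeguards already stand before the Month 24 injection. It is optional and needs new consent. The original criteria must be met again, including the contraception agreement, no contraindication to MRI, and ability to undergo the transplantation. The investigator then examines the subject and obtains laboratory work and imaging. A known or suspected pregnancy has several chances to surface. This stands, and it narrows the gap to an unrecognised pregnancy in a subgroup that chooses re-injection. That is the case a urine test is for.

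A second reply is that the test may be required in text not available here: the consent pages with their extension addendum, the body of Appendix C, the figure after the schedule, or the allograft instructions for use. Sites may also test under local practice. This stands as a limit. A reader might infer that subjects went untested, and the documents do not support that. They show only that the visible plan does not require the test.

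Three other inferences go too far:

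- **That everyone seen late in the VA6 window has outlived the no-planned-pregnancy period.** That period runs 24 months from treatment. A subject who crossed over at month 3 and is seen at months 24 to 27 after inclusion is 24 − 3 = 21 to 27 − 3 = 24 months past treatment, so not beyond it.
- **That the planned numbers measure exposure.** The totals of about 220 (all randomized, section 7.1.7) or 140 + 40 = 180 (active plus placebo, section 6.4) include men, subjects unable to conceive, and those who decline or fail the re-check.
- **That the crossover is either fully covered or plainly uncovered.** The label implies a test and the text does not state one.

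**Conclusion.** The point holds on the visible text. Appendix A schedules two injection visits and attaches a pregnancy test to one of them, and nothing visible adds it to the other. Because section 8.6 says the schedule holds all required assessments, a blank cell tells the site that none is required. The eligibility re-check is a partial safeguard and does not detect an existing pregnancy.

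The size cannot be given as a count. The documents state neither the number injected at Month 24 nor the share able to conceive. The gap is confined to the optional extension and lies outside the 12-month efficacy analysis, so endpoints, power and alpha are untouched. It should be corrected because it concerns subject safety and costs very little. The conclusion assumes that the material not visible here does not already require the test.

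**What to change.** 1. In Appendix A, mark the pregnancy-test row at VA6 with footnote f.
2. Add *urine pregnancy test, if applicable, before the injection* to footnote f, section 7.1.7 and the matching sentence in section 6. If the injection is given at the second office visit, do the test at that visit.
3. State the test explicitly for the conservative-care crossover in section 7.1.4 and footnote c, instead of relying on the new Day 0 label.
4. Apply one rule, *do not inject if positive*, to every injection. The simplest way is to add pregnancy to the exclusions in section 8.2 and the synopsis, since these are re-checked at VA6. Name the rule in the crossover text as well. Adding it at Month 24 alone would leave the other injections with a test and no stated action.

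The cost is one urine test per applicable subject injected at Month 24, with no extra visit, plus short text edits that go to the ethics committees as an amendment under section 15.1. If the test is already required in a document not visible here, the change only brings the schedule into line with it.
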